**1.0 Purpose of the study:**

**Aim 1 will characterize PD-MCI (Parkinson's disease mild cognitive impairment), PDN (Parkinson's disease without cognitive impairment), and HA (healthy adult) spoken discourse, cognitive, and motor speech profiles.** Phase 2 biomarker development requires robustly characterized cohorts in which to test candidate biomarkers. Using a standardized battery of cognitive, language, and motor speech tests PD participants will be assigned to PD-MCI (single/multi-domain) or PDN groups. We propose collecting spoken discourse samples using standardized elicitation protocols. The same tasks will be extracted from the extant HA database. Researchers will transcribe, code, and analyze discourse samples. Group differences (including sub-analyses for single and multi-domain MCI subtypes), elicitation stimuli effects, and group x stimuli interactions will be examined using multivariate and mixed-design ANOVA procedures.

**Aim 2 will develop and evaluate the classification accuracy of an optimally weighted discourse classification function for PD-MCI and PDN.** We propose using discriminant function analysis to identify an optimized composite variable that best predicts PD-MCI, PDN, and HA group membership. Sensitivity/specificity analyses, positive/negative predictive values, and receiver operating characteristic curves will be used to evaluate the discourse classification function properties.

The **primary endpoint** is an optimally weighted discourse function that can classify PD-MCI with > 80% sensitivity/specificity.

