## **4.0 Sample Size:**

We will enroll 86 PD participants (43 individuals with PD and normal cognition and 43 individuals with PD mild cognitive impairment). Data from 43 age/education/sex matched HA will be sampled from an extant repository.

Sample sizes for ANOVA and DFA were calculated using G\*Power. For Aim 1, a sample of 129 participants for MANOVA procedures with 3 IVs (PD-MCI, PDN, HA), 15 dependent variables (6 canonical variables), and up to 3 covariates will detect a minimum of  $f^2$  of 0.16 (medium-sized effects) with power of 0.90, and  $\alpha=0.05$ . The available effect size estimates for the 8 candidate discourse variables range from  $f^2$  of 0.33 to 0.50 (medium to large effects). With the smallest anticipated effect size based on our pilot data ( $f^2 = .33$ ) 129 participants in a mixed ANOVA with 2 IVs (Group [3 levels]) and Task [2 levels]) with up to 2 covariates will yield power of 0.86,  $\alpha=0.05$ . At the highest estimated effect size ( $f^2 = .50$ ), the same sample size will yield power of 0.99,  $\alpha=0.05$ . For **Aim 2**, DFA procedures with 3 groups and 8 discourse variables with 129

participants will detect  $f^2$  of .10 (small-medium effects) with power of 0.90,  $\alpha=0.05$  and power of 0.85, if  $\alpha=0.025$ . For the sensitivity and specificity analyses a sample of 129 participants will detect sensitivity and specificity values of 0.83 or higher with a 90% confidence interval precision of 0.10, given an expected disease (PD-MCI) prevalence of 30%, a conservative prevalence estimate. This precision level is consistent with guidelines for Phase 2 studies.

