**Aim 1**

Multivariate ANOVA statistical procedures will be used to examine group differences on neuropsychological test measures and spoken discourse measures. Follow-up univariate ANOVAs and Tukey's post-hoc tests will be used to further examine significant individual variables from the multivariate testing and to examine group contrasts (healthy controls, PD without cognitive impairment, and PD-MCI). If required based on group differences in descriptive variables age, sex, depression measure scores, and education will be entered as covariates.

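### Section 4.0: with 129 participants, f² = 0.33 gives mixed-ANOVA omnibus power above 0.999, not the stated 0.86, so the effect-size scale or the power figure is wrong

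*Combined protocol and SAP*

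**What the plan says.** Section 4.0 plans three groups of 43: "We will enroll 86 PD participants (43 individuals with PD and normal cognition and 43 individuals with PD mild cognitive impairment") and, for the healthy adults, "Data from 43 age/education/sex matched HA will be sampled from an extant repository". It reports pilot effects for the eight candidate discourse variables as f² from 0.33 to 0.50. It then gives two power figures at α = 0.05:

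- At f² = 0.33, introduced by "With the smallest anticipated effect size based on our pilot data", the stated result for N = 129 is that the planned "mixed ANOVA with 2 IVs (Group [3 levels]) and Task [2 levels]) with up to 2 covariates will yield power of 0.86".
- At f² = 0.50, "the same sample size will yield power of 0.99".

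The section names G*Power as the software. For this calculation it does not give the procedure, the effect tested, the numerator df or the correlation between the two tasks. Section 1.0 does not settle which effect was meant, because Aim 1 covers group differences and also "elicitation stimuli effects, and group x stimuli interactions will be examined using multivariate and mixed-design ANOVA procedures". In the data analysis part of section 8.0, Aim 1 adds that Tukey's "post-hoc tests will be used to further examine significant individual variables from the multivariate testing and to examine group contrasts".

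**The concern.** An f² of 0.33 is f = 0.574, a large standardised effect. With 43 people in each of three groups, an omnibus F test should detect it almost with certainty, so power of 0.86 looks far too low. Either the effect sizes are on a different scale from the one written, or the power figure belongs to some other test.

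The pilot effects are the empirical basis for this part of the sample-size argument. If 0.33 is f and not f², the smallest anticipated effect is f² = 0.33² = 0.109, about a third of the value written. A reader cannot tell which number to trust. Nor can the reader judge how well the study can separate PD-MCI from PDN and from healthy adults in the pairwise comparisons.

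**Working it through.** **Inputs.** From section 4.0: N = 129 (43 per group), Group 3 levels, Task 2 levels, up to 2 covariates, α = 0.05, f² = 0.33 and 0.50. Not given: the effect tested and the between-task correlation ρ.

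**Method.** Power = P(F′ > F_crit), with F′ noncentral F on df1 and df2 and noncentrality λ. Results use df2 = 124; values from 121 to 126 make no material difference. For two repeated measures, with f² defined on the single-measure scale:

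- group: λ = f² × N × 2/(1 + ρ)
- task and group × task: λ = f² × N × 2/(1 − ρ)

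Both multipliers are at least 1 for every possible ρ, so λ ≥ f² × N. The unstated correlation can only raise λ above this floor.

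**Step 1: the stated figure, inputs as written.** λ = 0.33 × 129 = 42.57.

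| df1 | 1 | 2 | 3 | 4 | 5 |
|---|---|---|---|---|---|
| Power, f² = 0.33 | 0.999997 | 0.99998 | 0.99994 | 0.99987 | 0.99975 |

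The stated 0.86 is not reproduced. In a 3 × 2 design, group has df 2, task df 1 and the interaction df 2; the other columns show that a different df would not help. A stricter convention, λ = 0.33 × 124 = 40.9, still leaves power above 0.9996. At α = 0.05/8, one test per candidate variable, it stays above 0.996 with λ = 42.57. A simulation of the group test gave 0.99995.

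**Step 2: what would give 0.86.**

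- At f² = 0.33 and df 2, a total N of 37 gives about 0.857 and 38 gives 0.867 to 0.868.
- At N = 129, f² must be 0.089 (f = 0.30) with df 2, or 0.111 (f = 0.33) with df 4.

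**Step 3: read the values as Cohen's f.** λ = 0.33² × 129 = 14.05, and λ = 0.50² × 129 = 32.25.

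| df1 | 1 | 2 | 3 | 4 | 5 |
|---|---|---|---|---|---|
| Power, f = 0.33 | 0.961 | 0.923 | 0.887 | 0.853 | 0.821 |
| Power, f = 0.50 | 0.9999 | 0.9995 | 0.9988 | 0.9978 | 0.9964 |

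For the group effect on the mean of the two tasks, f = 0.33 gives 0.94 to 0.99 (assumed ρ from 0.9 to 0.3). This reading comes much closer to the stated pair 0.86 and 0.99, but does not reproduce 0.86 for an effect of the 3 × 2 design.

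**Step 4: is f² used correctly elsewhere in section 4.0?** For the Aim 2 DFA (3 groups, 8 variables, f² = 0.10, λ = 2 × 129 × 0.10 = 25.8), power is 0.905 at α = 0.05 and 0.846 at α = 0.025, against 0.90 and 0.85 stated. Those figures reproduce on the f² scale, so the mismatch is not a matter of notation throughout the section.

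**Step 5: consequence for pairwise contrasts.** Assume equally spaced group means, 43 per group and one measure per person. The adjacent-group difference is d = √(1.5 × f²), with noncentrality d × √(43/2) on 124 df.

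| Reading of 0.33 | d | Unadjusted | Tukey |
|---|---|---|---|
| f² = 0.33 | 0.70 | 0.90 | 0.81 |
| f = 0.33 (f² = 0.109) | 0.40 | 0.46 | 0.31 |

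**The case against.** The mismatch itself is hard to dispute. The case on the other side concerns its explanation and its weight.

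- **The f reading is unproven.** This stands. No single effect in a 3 × 2 design has df 4, so the near-match of 0.853 is weak support, and the actual group test gives 0.92. The point rests on the inconsistency in Step 1, not on this explanation.
- **The contrast figures depend on the pattern of means, which the documents do not give.** This stands in part. If f = 0.33 and one group differs from two equal groups, that group's contrasts have power 0.81 (Tukey) to 0.90. With equal spacing, the extreme-group contrast has 0.91 to 0.96. Averaging two tasks (assumed ρ = 0.5) lifts the adjacent contrast to 0.42 (Tukey) and 0.57. The gap between the readings remains when the pattern is held fixed, however: with one group differing, f² = 0.33 gives over 0.999.
- **A contrast might explain 0.86.** Section 4.0 describes none for this calculation, and the adjacent contrast at f² = 0.33 gives 0.90 or 0.81.
- **Little hangs on it.** N = 129 suffices for the omnibus test on either reading, 0.86 is conservative if f² is right, and the primary endpoint, classification accuracy, is sized separately. All true. This limits the point to a correction of the justification; it does not make the stated figure right.

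**Conclusion.** The concern holds. With 129 participants and α = 0.05, f² = 0.33 implies omnibus power above 0.999 for every effect that the design defines, against 0.86 stated. No choice of task correlation, up to two covariates, numerator df from 1 to 5, or eightfold Bonferroni adjustment closes that gap. At least one of the two numbers is wrong as written.

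That the pilot values are really Cohen's f is the more plausible reading but remains an inference. The two readings differ threefold in effect size (f² of 0.33 against 0.11). This is not evidence of too small a sample for the omnibus tests. It leaves power for adjacent-group comparisons unknown: 0.81 or 0.31 with Tukey, under equally spaced means and one measure per person.

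**What to change.** In section 4.0:

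1. State whether the pilot effects of 0.33 to 0.50 are f or f², checked against the pilot output.
2. Name the effect that the power refers to (group, task or group × task), its numerator df and the assumed between-task correlation.
3. Rerun the calculation and restate whichever figure is wrong. If f² is right, power is above 0.999 at both effect sizes. If f was meant, relabel the range as f = 0.33 to 0.50 (f² = 0.11 to 0.25) and report the recomputed power for the named test. For orientation, a plain df-2 group test at f = 0.33 has about 0.92.

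The cost is one rerun and a correction to two sentences. Enrolment does not change, and the MANOVA and DFA calculations are not touched by this point.

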## 5.0 Research Locations:

### New Data Collection

All data collection will take place at Northwestern University, Evanston campus, the Northwestern University Department of Communication Sciences and Disorders flexible laboratory research space located in Abbott Hall on the Chicago campus, or alternatively in participant homes through in-person or virtual visits if individuals are not able to physically travel to our locations.

Data will be collected in a dedicated research space (or participant home). Data will be collected in a low distraction, accessible environment specifically designed for the collection of discourse and neuropsychology testing data. If data are collected in a participant's home, efforts will be made to create a low-distraction quiet environment consistent with the research spaces located on the Evanston and Chicago campuses.

Data will also be collected virtually through Zoom videoconferencing. Similar efforts to in-person data collection in participants' homes will be made to replicate low-distraction environments consistent with the research spaces on the Evanston and Chicago campuses. A HIPAA-compliant, end-to-end encrypted version of Zoom will be used for study visits to comply with strict personal health information protection guidelines. If participants do not have access to a personal computer capable of running the necessary videoconferencing software, a microphone for audio recording, or a webcam for videorecording we mail or drop off necessary hardware to their homes.

### Extant Data Collection (Healthy Adult data)

Demographic data and neuropsychology testing measures for the healthy control sample will be secured from an extant dataset in a secure repository ICPSR 3664 (Harris Wright, Heather, and Capilouto, Gilson J. Discourse Processing in Healthy Aging in the United States. Ann Arbor, MI: Inter-university Consortium for Political and Social Research [distributor], 2017-03-02. <https://doi.org/10.3886/ICPSR36634.v1>). Audio and video files of spoken discourse samples for the same study (study of normal aging and discourse) are curated with the Carolina Conversations Collection and are available for use in research with an approved IRB (<http://carolinaconversations.musc.edu/about/>).

## 6.0 Multiple sites:

Shirley Ryan AbilityLab – [name] who has faculty appointments at both NU Evanston (Communication Sciences and Disorders) and the Shirley Ryan AbilityLab is a co-investigator. [name] involvement is limited to providing mentorship to the PI on grant administration, serving in a consultative role for resolving discourse coding ambiguities, and supporting the PI in interpreting the study results. While [name] may have a limited role in recruiting participants with Parkinson's disease, no data will

be collected from, nor will any health records be required from, the Shirley Ryan AbilityLab.

Feinberg – [name] is on faculty at Feinberg. [name] will be involved with recruiting (not enrolling) participants. She will also be involved with the design of the study and the interpretation of the results. [name] will also provide medical guidance and PD expertise as required during the study. The study does not require access to patient records at NMH.

## **7.0 Reliance Agreements/Single IRB:**

NU is the IRB of record for both the Shirley Ryan AbilityLab and Feinberg. To the PIs knowledge no additional IRB permissions or reliance agreements are required.

## **8.0 Procedures Involved:**

The proposed study is not a clinical trial and was not deemed as such by the NIH.

## **C. APPROACH**

Observational, cross-sectional study with three cohorts: healthy older adults, individuals with Parkinson's disease without cognitive impairment, and individuals with Parkinson's disease with mild cognitive impairment.

### **Data Sources**

Measures collected **on all PD participants**. Only PD participants will be recruited locally. All healthy control data will be extracted from extant databases available through data sharing agreements or publicly accessible datasets. All measures will be audio and video recorded in order to facilitate off-line data analysis for standardized measures and orthographic transcription of discourse samples. If the participant has completed any of the neuropsychological testing measures in our lab within the last 6-months, and a suitable alternate version of that test is not available, we will use their previous data in order to reduce participant burden and data contamination (e.g., learning effects from previous test administrations).

In the PD group measures will be collected over 1 or 2 visits (conducted within a 4-week window), depending on participant fatigue levels/scheduling. Each participant's total involvement is anticipated at 3 to 3.5 hours in duration. The typical participant is anticipated to complete the protocol in one visit.

All tests will be administered by trained research staff. All measures will be administered and scored in accordance with their published manuals/scoring instructions.

Participants may complete the protocol in our Evanston lab, satellite lab in Abbott Hall, or their home through in-person or remote visits. Participants will be able to select a time of day of their choosing for completing the protocol.

The total duration of the research project is estimated at 36 months.

The study visit will be conducted in two stages: a screening portion and the experiment portion. With the exception of the cognitive testing, hearing testing, and vision testing all other inclusion criteria will be evaluated during the initial phone, email, or in-person contact with the participant when interest in the study is expressed.

Participants will receive reminder calls regarding upcoming appointments. These will typically occur within 72 hours of the scheduled appointment. During the telephone

Descriptive Variables
Geriatric Depression Scale – brief depression screening tool. Depression can interact with language production abilities.
MDS-Unified Parkinson Disease Rating Scale – measure of PD motor symptoms. Completed through physical exam by a certified research assistant or the PI.
Hoehn and Yahr scale – PD staging tool completed as part of the motor exam
Communication Participation Item Bank measure – pen and paper tool measuring communication quality of life

reminder call, staff members will complete the Participant/Visitor health screener for (attached to protocol). If participants answer ‘yes’ to any item, staff members will request that their study visit be rescheduled at a time that is convenient for the participant. If the participant answers ‘yes’ to any of the questions under the ‘Travel’ heading then they will be provided with the COVID-19 contact information handout (attached). This information will be emailed to the participant if required. Information will also be provided over the telephone including the email and telephone contacts for the Illinois Department of Public Health.

If the participant cannot be contacted by telephone, the screening form can be completed in person at the time of the study visit (but prior to initiating any substantial participant contact). Visitors who accompany the participant will also be asked to complete a health screener, if they intend to wait in the research lab lobby space. Health screening tools will be stored in a locked filing cabinet in the PIs lab for a period of 60 days following the participant’s visit. Following this period, forms will be shredded using secure shredding boxes located in the NUCASLL clinic/Pis home department (CSD).

During the **screening portion** of the visit, participants will complete the Montreal Cognitive Assessment (MoCA), an audiometric hearing assessment, and a vision screening using a Snellen eye chart. Participants meeting the inclusion criteria for the study will advance immediately to the experiment tasks. Those not meeting the inclusion criteria will be provided summary results, including the criteria that they did not meet (i.e., cognition, hearing, vision) and will be advised to discuss these results with their healthcare team.

During the **experiment portion** of the visit participants will complete the following tasks:

Descriptive and Neuropsychological Testing Measures – The measures in the table below are standard descriptive measures for the population and the research aims under study. These are all standard clinical measures in PD clinical practice. Standardized language and cognitive neuropsychological measures will be used to stratify participants into PD-MCI and PD normal cognition groups using the Movement Disorders Society Task Force published guidelines.

Sentence Intelligibility Test (SIT-5). Set of 11-sentences generated for each participant. Sentences are phonetically balanced and are read aloud by the participant. Measure of speech intelligibility
Standardized oral reading passage (speech rate and intelligibility)
Brief motor speech exam
Demographic form (attached)
National Adult Reading Test
Neuropsychological Measures Used in Primary Analyses and to Classify Participants into MCI-PD from PDN (no cognitive impairment) groups
Trail Making Test-A (In-person testing)
Trail Making Test-B (In person testing)
10-points Clock Drawing Test + Clock copying
Free and Cued Selective Reminding Test from the Arizona Battery of Communication Disorders of Dementia (In-person testing)
Brief Visuospatial Memory Test-Revised
Semantic Fluency-animals
Digit span forward and backward
Stroop Color-word Interference
Boston Naming Test (30-item version)
Verb Naming Subtest – Northwestern Assessment of Verbs and Sentences
Sentence Production Priming subtest of the Northwestern Assessment of Verbs and Sentences
Pyramids and Palm Trees Test - object semantics
CERAD 10-Word List (Remote testing)

Discourse Sampling (main study outcome measure)

Using standardized spoken discourse elicitation stimuli and instructions, participants will be asked to generate a story about a series of events occurring in: 1) a series of six black and white line drawings and 2) a wordless picture book. Participants will generate a maximum of four spoken discourse samples. Each discourse sample is estimated at 2 to 4 minutes in length. Audio files will be transcribed using a HIPAA compliant transcription service/software. Once transcribed, files will be coded in [name] lab for a number of discourse (e.g., story structure, information content), speech (e.g., pauses, number of words), and language variables (e.g., grammar/syntax).

Proposed Data Analysis

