### 3.0 Inclusion and Exclusion Criteria:

Only individuals with PD will be newly recruited and enrolled as part of the study. Healthy adult data will be extracted from extant databases (publicly available) from NIH-funded studies.

Inclusion Criteria Person with Parkinson's disease without cognitive impairment

- Age 50-90 years
- Diagnosis of idiopathic Parkinson's disease (UK Brain Bank criteria) made by a movement disorders specialist
- Under the care of a movement disorders specialist for a minimum of 1-year duration
- Native monolingual English speaker
- Hoehn & Yahr score between 1.5 and 4
- Grade 10 education, or higher
- Sufficient vision and hearing (aided or unaided) for all experiment tasks
- Montreal Cognitive Assessment (or MoCA-converted MMSE score) greater than or equal to 25
- No subjective complaints of cognitive difficulty or word finding issues

Inclusion Criteria Person with Parkinson's disease mild cognitive impairment

- Age 50-90 years
- Diagnosis of idiopathic Parkinson's disease (UK Brain Bank criteria) made by a movement disorders specialist

- Under the care of a movement disorders specialist for a minimum of 1-year duration
- Native monolingual English speaker
- Hoehn & Yahr score between 1.5 and 4
- Grade 10 education, or higher
- Sufficient vision and hearing (aided or unaided) for all experiment tasks
- Montreal Cognitive Assessment (or MoCA-converted MMSE score) greater than or equal to 17
- Subjective complaints of cognitive difficulty or word finding issues, without significant impact on activities of daily living

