**Inclusion Healthy Adults (from extant data base – no new recruiting)**

- Age 50-90 years
- Montreal Cognitive Assessment (or MoCA-converted MMSE score) greater than or equal to 26
- Native monolingual English speaker
- Grade 10 education, or higher
- Sufficient vision and hearing (aided or unaided) for all experiment tasks

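### Aim 1 tests PD-MCI against PDN for significance on the same neuropsychological battery that assigns participants to those two groups, so the battery p-values are not independent evidence that the groups are distinct

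*Combined protocol and SAP*

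**What the plan says.** Three places make the battery the classifier. Section 1.0, under Aim 1: "Using a standardized battery of cognitive, language, and motor speech tests PD participants will be assigned to PD-MCI (single/multi-domain) or PDN groups". Section 8.0, Data Sources: "Standardized language and cognitive neuropsychological measures will be used to stratify participants into PD-MCI and PD normal cognition groups", following outside task-force guidelines whose cut-offs are not reproduced. The table in Section 8.0 lists 13 measures under the label "Neuropsychological Measures Used in Primary Analyses and to Classify Participants into MCI-PD from PDN (no cognitive impairment) groups".

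The Aim 1 paragraph of the Proposed Data Analysis then makes the same measures outcomes: "Multivariate ANOVA statistical procedures will be used to examine group differences on neuropsychological test measures and spoken discourse measures". Univariate ANOVAs follow, and Tukey's "post-hoc tests will be used to further examine significant individual variables from the multivariate testing"; the contrasts named there are among healthy controls (HA), PDN and PD-MCI. No text sets aside separate tests for classification, limits the battery comparison to description, or mentions the overlap. Yet Data Sources introduces the table this way: "The measures in the table below are standard descriptive measures for the population and the research aims under study".

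Section 4.0 plans 43 participants per group (129 in all). It powers the Aim 1 MANOVA on 15 dependent variables and speaks of 8 candidate discourse variables.

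**The concern.** If people are labelled PD-MCI because they score low on certain tests, the PD-MCI group must have lower means on those tests. Equality of the PD-MCI and PDN means is then false before any data are seen, and rejecting it says nothing about whether the battery has found two distinct kinds of patient. The three-group MANOVA and ANOVAs inherit the problem because they contain that contrast.

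PDN versus HA on the battery is shifted too, since PDN are chosen for not being impaired on it.

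At stake is the cognitive half of Aim 1. Small p-values on the battery could be read as validating the cohorts in which the biomarker is tested. If battery and discourse measures share one MANOVA, which the plan leaves open, the classifying tests could also make that MANOVA significant and so open the way to the discourse follow-up tests.

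**Working it through.** **1. The plan's own figure.** Section 4.0 states power 0.90 for N = 129, 3 groups, 15 dependent variables, up to 3 covariates, f² = 0.16, α = 0.05. Pillai trace, noncentral F:

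- s = 2; df1 = 15 × 2 = 30; df2 = s(N − groups − covariates − p + s) = 2(129 − 3 − 3 − 15 + 2) = 220
- λ = df2 × f² = 220 × 0.16 = 35.2; power = 0.919

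This is within 2 points of 0.90. The calculation is not at fault, but for battery outcomes it does not measure a chance of discovery.

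**2. Inputs for the illustration.** From the documents: 43 per group; Tukey and MANOVA at 0.05; of the 13 listed measures, the in-person and remote labels leave 12 in person and 10 remotely. Assumed, because the documents give no values: PD-MCI if at least 2 tests fall below −1, −1.5 or −2 SD; equicorrelated normal scores with correlation 0 to 0.5; one homogeneous PD population with no true subgroups; HA with the same true means.

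**3. One case by hand.** K = 10 tests, correlation 0, cut-off c = 1.5. Then p = Φ(−1.5) = 0.0668 and the normal density φ(1.5) = 0.1295.

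- Share labelled PD-MCI: 1 − 0.9332¹⁰ − 10 × 0.0668 × 0.9332⁹ = 1 − 0.501 − 0.359 = 0.141
- Mean shift carried by the label: A = φ(c)(K − 1)p(1 − p)^(K−2) = 0.1295 × 9 × 0.0668 × 0.9332⁸ = 0.0448
- PD-MCI mean per test: −0.0448/0.141 = −0.32 SD; PDN mean: +0.0448/0.859 = +0.05 SD; gap about 0.37 SD
- Expected t: 0.37/√(2/43) = 0.37/0.216 = 1.7, against a Tukey critical value of about 2.37 (126 df)

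A single test therefore rejects only about a quarter of the time here. The MANOVA accumulates all ten gaps (sum of squares about 10 × 0.37² = 1.4) and rejects almost always.

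**4. Simulation over the range of assumptions.** Rejection columns are for 10 or 12 tests; gaps are for 10, 12 or 13 tests.

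| Inter-test correlation | Built-in PD-MCI vs PDN gap per test (SD) | Tukey rejection per test | Three-group MANOVA rejection |
|---|---|---|---|
| 0 | 0.29-0.46 | about 17-33% | about 89-100% |
| 0.1 | 0.53-0.76 | about 57-83% | at least 99% |
| 0.2 | 0.71-1.00 | 86-98% | at least 99% |
| 0.3-0.5 | 0.86-1.52 | 98-100% | at least 99% |

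With labels assigned at random, Tukey rejects about 2% per test and the MANOVA 4-5%. The largest gaps come from the −2 SD cut-off, which labels only about 2-6% of the PD population PD-MCI; Section 4.0 uses a PD-MCI prevalence of 30%.

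**5. Entry criteria.** The PD-MCI criterion is "Montreal Cognitive Assessment (or MoCA-converted MMSE score) greater than or equal to 17"; PDN need at least 25. With MoCA floors modelled (percentiles assumed), Tukey rejection is 15-33% at correlation 0 and 98-100% at 0.3-0.5, essentially unchanged.

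**6. PDN versus HA.** With equal true means, PDN minus HA is shifted by 0.01 to 0.46 SD if HA are unselected. HA are in fact screened ("Montreal Cognitive Assessment (or MoCA-converted MMSE score) greater than or equal to 26"); with that modelled the shift is −0.06 to 0.28 SD. Its size, and in some cases its sign, depends on the assumptions.

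**The case against.** The strongest reply is that comparing groups on their defining tests is routine characterization. It confirms that assignment worked, and which domains fall low remains informative. No decision depends on these p-values: discourse is the main outcome and the primary endpoint is the Aim 2 function. This stands as a case for describing the battery and as a limit on how much the point matters. It does not rescue the significance tests, which the plan specifies without exemption on measures it labels as part of the primary analyses.

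Three stronger readings are tempting.

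- *The battery results would be false positives.* They would not. The groups as defined by the rule do have different means; the rejections are true but uninformative about distinct subgroups.
- *Every battery test would come out significant.* Per-test rejection is near-certain only at correlations of about 0.2 or more, and the documents give no correlation. Only the MANOVA is near-certain across most of the range.
- *The discourse results are contaminated.* The Aim 2 discriminant analysis uses discourse data only. The Aim 1 discourse tests are also clear if they have their own MANOVA. The 15 dependent variables set against 8 discourse candidates are consistent with battery tests being among the powered outcomes, but the text does not say so.

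**Conclusion.** The point holds for the neuropsychological part of Aim 1. The overlap is in the plan's own words, and the direction of the effect needs no assumption: grouping on low scores makes the PD-MCI versus PDN p-values on those scores, and the three-group p-values containing them, too small. They are not independent evidence that the groups are distinct. The sizes (about 89-100% for the MANOVA, and from 17-33% to 98-100% per test) rest on assumed cut-offs, equal correlations, normal scores and no true subgroups; they illustrate the mechanism and do not forecast this study's results. The primary endpoint is not directly affected. The change is worth making because the plan specifies an analysis whose significance cannot be interpreted, and the remedy is cheap.

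**What to change.** 1. In the Section 8.0 table and the Aim 1 analysis text, state that the classifying tests will be reported descriptively by group (normed z-scores, means, confidence intervals), with no PD-MCI versus PDN significance tests on them. Label any HA contrast on these tests as affected by the selection of the PD groups.
2. State that the inferential Aim 1 MANOVA uses the discourse variables alone, so that classifying tests cannot open its gate.
3. Restate the Section 4.0 calculation for the discourse variables actually tested. If these are the 8 candidates, the method of step 1 of the working, with 3 covariates and f² held at 0.16, gives df1 = 16, df2 = 2(129 − 3 − 3 − 8 + 2) = 234, λ = 37.44 and power of about 0.99, so the sample size is not threatened.

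The cost is the loss of uninformative battery p-values and the redrafting of Section 4.0. No new data are needed.
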